The primary outcome measure of this study will be the initial difference in pressure between the medial and lateral compartments at 10 degrees of flexion (10-degree pressure delta). Because the compartment pressures will be assessed by both the operating surgeon and an assistant, the mean difference of the two readings will constitute the primary outcome measure.

Secondary Outcome Measures

Knee-Specific Outcome Scores

- *Knee injury and Osteoarthritis Outcome Score (KOOS - www.koos.nu)* - The KOOS score is a patient-administered instrument widely used to assess patients' opinions about their knee pain and function. It consists of five

subscales: Pain, other Symptoms, Activities of Daily Living (ADL), Sport and Recreation (Sport/Rec) and knee-related Quality of Life (QOL). A normalised score is calculated for each subscale, with 100 indicating no symptoms and 0 indicating extreme symptoms. The minimum clinically important change in KOOS has been defined as 8-10 points on a 100-point scale with a reported standard deviation of 16 [28, 29]. We will use the mean of the 3 subscale scores - KOOS Pain, KOOS Symptoms and KOOS ADL with the primary outcome end point will be change in the mean KOOS from pre-operative scores and 12 months. The KOOS at six months, two years, five years and 10 years will also be recorded. We will also analyse each of the five subscale separately as secondary endpoints.

- *Forgotten Joint Score - Knee (FJS-12 Knee - <http://www.forgotten-joint-score.info/knee>)* - The FJS-12 is a patient-reported tool that was designed to assess patient outcome in patients undergoing conservative or operative treatment of the knee, and focuses on patients' awareness of their knee in everyday life. Joint awareness can be defined as any unintended perception of a joint. This may include strong sensations like pain, but also includes more subtle feelings like mild stiffness, subjective dysfunction, or any discomfort. Generally, joint awareness comes with a negative connotation as healthy joints do not cause 'awareness' in daily life – and are essentially 'forgotten'. The FJS-12 Knee has low ceiling effects, allowing monitoring of longer term outcomes, particularly in well-performing groups after total joint arthroplasty [30]. The FJS-12 will be measured pre-operatively and at one year and two years post-operatively.

Quality of Life Measures

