For the secondary outcome measures, however, strategies for improving adherence to protocol include clear elucidation during the consenting process of the importance of committing to the schedule of follow-up visits, PROMs, and x-rays. Participants will have an opportunity to ask questions, and key messages about the study will be reinforced, at each follow-up visit. In order to prevent missing data and avoid associated complexities in study analysis and interpretation, administrative systems will be employed to diligently schedule follow-up appointments, provide reminders and monitor retention. It is projected that the rate of loss to follow-up for the secondary objectives will be no more than 5%.

Complications

Complications to be recorded will include intra-operative complications, Serious Adverse Events related to the index operation and Adverse Events unrelated to the operation, as defined by the ACORN registry (Table 1). Post-operative complications will be assessed and recorded at all follow-up time points (Table 3), and as necessary at unscheduled times.

Patient-reported outcomes will be monitored throughout the study to supplementally inform the clinical care of individual participants, but their timing coincides with scheduled clinical assessment in any case.

Radiographic Measures

Radiographic investigation will be defined by CT Perth Protocol [31, 32]. This will include HKA Angle, LDFA and MPTA, as well as femoral and tibial component sagittal and rotational position. A routine series of radiographs (AP erect, lateral and skyline views) will also be performed pre-operatively, at six months and two years.

Intra-operative Outcome Measures

Tibiofemoral Compartmental Pressure Loads - Initial medial and lateral compartmental pressure and final medial and lateral pressure loads will be

compared in both groups at 10°, 45° and 90° of knee flexion. Optimal knee balance will be defined as a pressure difference of less than 15 lb between compartments at 10°, 45° and 90° of knee flexion, with no pressure exceeding 40 lbs.

Functional Outcome Measures

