Normality of data distribution will be assessed and the Student's t-test will be used to compare differences in means with continuous variables. The Chi-squared test and Fishers exact test will be used for categorical data analysis as appropriate. Intention-to-treat analysis will be performed in the primary analysis. In addition, a per-protocol analysis including participants according to treatment received will also be added as a secondary analysis. Analysis of secondary outcomes will include mixed-model

analyses comparing secondary outcomes between time points. If greater than 20% of data is missing from the randomised sample, the missing data will be imputed. However, attempts will be made to minimise missing data by contacting patients directly by phone or via mail follow-up.

ETHICS AND DISSEMINATION

Safety considerations

Because the two groups being analysed will both be offered current routine standards of care, we do not anticipate that either the intervention or control arm will be associated with any adverse events beyond those to which patients are normally exposed during total knee arthroplasty surgery.

The trial will be conducted at St George Private Hospital (Kogarah, NSW) which has provisions for liability insurance. There will be specific information included in the Patient Information Sheet and Consent form instructing the participant to notify the principal investigators of any adverse events or complications that arise during the course of the trial.

Ethics

This study protocol was approved by the ethics committee of Bellberry Limited on 16 January 2018 (#2017-12-911) and was registered with the Australian New Zealand Clinical Trials Registry (#ACTRN12617001627347p).

Important modifications to the protocol that may impact the conduct of the study (including changes of study objectives, study design, patient population, sample sizes, study procedures or significant administrative aspects) will be communicated to Bellberry Limited and the St George Private Hospital governance board as necessary for their approval. Administrative changes of the protocol are minor corrections and/or clarifications that have no effect on the way the study is to be conducted.

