	18b	Plans to promote participant retention and complete follow-up, including list of any outcome data to be collected for participants who discontinue or deviate from intervention protocols	Specification of PRO data collection management strategies for minimising avoidable missing data. Description of process of PRO assessment for participants who discontinue or deviate from the assigned intervention protocol.	16
Data management	19	Plans for data entry, coding, security and storage, including any related processes to promote data quality (e.g. double data entry, range checks for data values). Reference to where details of data management procedures can be found, if not in the protocol		20
Statistical methods	20a	Statistical methods for analysing primary and secondary outcomes. Reference to where other details of the statistical analysis plan can be found, if not in the protocol		18
	20b	Methods for any additional analyses (e.g. subgroup and adjusted analyses)		N/A
	20c	Definition of analysis population relating to protocol non-adherence (e.g. as randomised analysis) and any statistical methods to handle missing data (e.g. multiple imputation)		18
Methods: Monitoring				
Data monitoring	21a	Composition of data monitoring committee; summary of its role and reporting structure; statement of whether it is independent from the sponsor and competing interests; reference to where further details about its charter can be found, if not in the protocol. Alternatively, an explanation of why a data monitoring committee is not needed		18
	21b	Description of any interim analyses and stopping guidelines, including who will have access to these interim results and make the final decision to terminate the trial		18
Harms	22	Plans for collecting, assessing, reporting and managing solicited and spontaneously reported adverse events and other unintended effects of trial interventions or trial conduct	State whether or not PRO data will be monitored during the study to inform the clinical care of individual trial participants, and if so, how this will be managed in a standardised way. Describe how this process will be explained to participants (e.g. in the Participant Information Sheet and Consent Form)	16, 19
Auditing	23	Frequency and procedures for auditing trial conduct, if any, and whether the process will be independent from investigators and sponsor(s).		18

Ethics and Dissemination

[figure not shown]
SPIRIT 2013 Checklist with SPIRIT-PRO Extensions

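### The secondary mixed model is described as comparing time points rather than arms, the 12-month KOOS comparison is an unadjusted raw change, and the 20% imputation trigger is arbitrary

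*Protocol*

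**What the plan says.** The Data Analysis section first gives general tests: "the Student's t-test will be used to compare differences in means with continuous variables", with chi-squared or Fisher's exact test for categorical data. It then continues: "Analysis of secondary outcomes will include mixed-model" "analyses comparing secondary outcomes between time points". No arm effect or arm-by-visit effect is named for that model.

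Under Secondary Outcome Measures, the KOOS paragraph averages the Pain, Symptoms and ADL subscales and says the "primary outcome end point will be change in the mean KOOS from pre-operative scores and 12 months". The trial's primary outcome is the intra-operative 10-degree pressure difference, so the word primary is misplaced there.

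On missing data, Data Analysis says: "If greater than 20% of data is missing from the randomised sample, the missing data will be imputed". No imputation method is named. The Secondary Outcome Measures text says: "It is projected that the rate of loss to follow-up for the secondary objectives will be no more than 5" per cent.

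The Sample Size section states the patient-reported aim as a comparison of KA with MA. It sizes KOOS at about 64 per group for an 8-point difference and an SD of 16. Table 3 schedules KOOS pre-operatively and at six months, one year and two years.

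**The concern.** A comparison between time points answers whether patients improve after knee replacement. The protocol already expects large improvement: it cites cohort KOOS changes of 37 to 45 points. The randomised question is whether the improvement differs by alignment method, and the sentence describing the repeated-measures model does not ask it.

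That leaves the arm comparison of 12-month KOOS to a t-test on raw change. Such a test gives up precision that the pre-operative score would supply, and it leaves chance baseline imbalance only crudely handled. KOOS has little margin: 64 per group is 128 patients, while the primary outcome sets the trial at 125.

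The imputation rule turns on the amount missing rather than on why data are missing. For a test at one time point it allows a sizeable group to drop out of the analysis with nothing further required.

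**Working it through.** **1. The plan's own KOOS figure.** Inputs from Sample Size: difference 8, SD 16, 5% significance (taken as two-sided), 80% power, 1:1.

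n per arm = 2 × (1.960 + 0.842)² × 16² / 8² = 62.8, so 63. The t-test calculation gives 63.8, so 64. The stated figure of about 64 is reproduced.

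**2. Patients available.** 125 × 0.95 = 118.75, about 119 completers, or 59.5 per arm.

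**3. Raw change against baseline adjustment.** Let r be the correlation between pre-operative and 12-month KOOS, with equal variances at both times. The protocol gives no r, so 0.3, 0.5 and 0.7 are assumptions.

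- Variance of change: 2σ²(1 − r)
- Variance after adjustment (ANCOVA): σ²(1 − r²)
- Ratio: (1 + r)/2 = 0.65, 0.75, 0.85

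Power = Φ(8 / (SD × √(2/59.5)) − 1.960). For SD 16 the standard error is 2.933, 8/2.933 = 2.727, and Φ(0.767) = 77.9%.

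The protocol does not say whether 16 is the SD of the change or of the score, so both readings are shown.

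| r | 16 = SD of change: raw change | adjusted (SD) | 16 = SD of score: raw change (SD) | adjusted (SD) |
|---|---|---|---|---|
| 0.3 | 77.9% | 92.3% (12.90) | 63.5% (18.93) | 81.6% (15.26) |
| 0.5 | 77.9% | 88.3% (13.86) | 77.9% (16.00) | 88.3% (13.86) |
| 0.7 | 77.9% | 84.1% (14.75) | 94.1% (12.39) | 96.8% (11.43) |

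These use the normal approximation. On the score reading, t-based values run up to about one point lower: 62.8% and 80.9% at r = 0.3, 77.2% and 87.8% at r = 0.5.

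**4. The imputation trigger.** At the projected loss, 5% is below 20%, so the rule is not triggered. At the threshold, 0.20 × 125 = 25 patients may be missing without imputation, leaving 50 per arm. With SD 16, power of the t-test on change is 79.8% with nothing missing, 77.8% at 5% and 70.5% at 20%.

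**The case against.** Several stronger conclusions are tempting, and the document does not support them.

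- **That the plan has no comparison of arms.** The t-test and the chi-squared or Fisher tests come first and can compare arms. The mixed-model sentence says what the analysis will include, which adds to those tests. The design is a superiority trial of KA against MA. What stands is that the mixed model is given a stated contrast, and it is not the randomised one.
- **That intention-to-treat is broken.** The protocol attaches intention-to-treat to the primary analysis. The primary outcome is recorded in theatre with no expected loss, so missing questionnaires cannot breach it there.
- **That up to 20% missing means complete-case analysis throughout.** The protocol does not say so. A likelihood-based mixed model would use incomplete records under missing at random. The point is confined to single-time-point tests such as the t-test on 12-month change.
- **That the rule can never operate.** The 5% is a projection, and the KOOS paragraph also plans recording at five and ten years.
- **That a bias can be stated.** If dropouts differed from completers by 10 KOOS points more in one arm than in the other, 20% missing would give 0.20 × 10 = 2 points, and the projected 5% would give 0.05 × 10 = 0.5. The 10 points have no source in the protocol, so neither figure is a finding.
- **That KOOS power is only 63%.** This needs 16 to be the SD of the score and r = 0.3.

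It is also fair to say that raw change is not an error, since randomisation keeps it unbiased. Model terms are often left to an analysis plan. The N/A at SPIRIT item 20b concerns additional analyses and does not by itself exclude the baseline score from the main model. These arguments limit the point to precision and wording. They do not make a time-point contrast answer the KA-MA question.

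**Conclusion.** The point holds for secondary outcomes only and should be corrected. The mixed model's described contrast does not match the stated patient-reported aim, and the arm comparison of KOOS is left to a less precise method than the scheduled data allow.

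Over r = 0.3 to 0.7, the gain from baseline adjustment is about 6 to 14 percentage points of power if 16 is the SD of change. If 16 is the SD of the score, it is about 3 to 18 points. The gain is positive on both readings; its size depends on the assumed r, on equal pre and post variances and on 5% loss.

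The 20% trigger is arbitrary and inactive at the projected loss. Its reach is the single-time-point tests, where up to 25 of 125 patients could be left out.

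**What to change.** - **Model.** For KOOS, analyse the post-operative scores with a likelihood-based mixed model containing arm, visit, arm-by-visit and pre-operative score, with a patient random effect, on all available data. Name the KA-MA difference at 12 months as the KOOS estimate. Use the same form for FJS (one and two years) and EQ-5D (six months and two years).
- **Missing data.** Delete the 20% threshold. Use the model whatever the amount missing, and multiple imputation as a sensitivity analysis for outcomes tested at a single time point.
- **Label.** In the KOOS paragraph, replace the primary label with a secondary one.
- **SD.** State whether 16 is the SD of the score or of the change.

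The cost is a few sentences of analysis wording and slightly more programming. No new data, visits or patients are needed.

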Appendix 1. Leg Positioning for VERASENSE™ Pressure Calculations

▶ **HOLDING THE LEG** For the correct depiction of intra-articular loading, in extension and flexion, the leg must be held with posterior support:

Step 1.
With the leg in extension, one hand is placed on the heel of the operative leg; one hand is placed under the backside of the knee, at the posterior capsule.

Step 3.
Soft tissues should continue to be evaluated at 45° (FIG A) and 90° of flexion (FIG B). If using a cruciate retaining component, an intraoperative posterior drawer test will allow the surgeon to assess PCL stability using the VERASENSE tracking option (FIG C).

Step 2.
Initial evaluation of soft tissue should always be assessed with the leg flexed in 10° with the posterior capsule relaxed and the screw home mechanism disengaged. Failure to do so could result in the over-releasing of soft-tissue, as loads tend to increase during terminal extension due to the screw home mechanism.

▶ **HOLDING THE LEG (CONTINUED)**

INCORRECT
Abducted/Externally Rotated

INCORRECT
Adducted/Internally Rotated

CORRECT
Neutral Position

[figure not shown]

[figure not shown]

[figure not shown]

SURGICAL TECHNIQUE QUICK REFERENCE

Authored By: **[name].**
Holy Cross Hospital, Fort Lauderdale, FL

[name].
NYU Langone Medical Center, New York, NY

Assess soft-tissue load references with **joint reduced and capsule closed**. Only address soft-tissues after loads have been assessed in both **extension and flexion (10°-90°)**. After any tissue release, the **leg should be "cycled"** (taken through the range of motion) several times.

APPROACH TO VARUS KNEE

▶ TIGHT IN EXTENSION - MEDIALY	▶ TIGHT IN FLEXION - MEDIALY	▶ TIGHT IN FLEXION AND EXTENSION - MEDIALY	

SENSOR PRESENTATION:
 	
SENSOR PRESENTATION:
 	
SENSOR PRESENTATION:
 	
SENSOR PRESENTATION:
 

SURGICAL CONSIDERATION:
 	
SURGICAL CONSIDERATION:
 	
SURGICAL CONSIDERATION:
 	
SURGICAL CONSIDERATION:
 

Evaluate MCL Palpate fibers of MCL to assess tension. Release posterior fibers of MCL (both deep and superficial).
 	
Condition 1. Evaluate MCL Palpate fibers of MCL to assess tension. Release anterior fibers of MCL (both deep and superficial).
 
SENSOR PRESENTATION:
 	
Condition 1. Loads 20-40 lbs. Extension Balancing:
 
 - Posterior MCL fibers released if in tension; loads rechecked. - Posterior medial capsule checked for tension and released, if needed; loads re-checked. - If necessary, semimembranosus can be released. 
Flexion Balancing:
 
 - Anterior MCL fibers released if in tension; loads rechecked. 	

Evaluate Medial Posterior Capsule Release medial posterior capsule and/or semimembranosus at tibial attachment site.
	
SURGICAL CONSIDERATION:
 	
Condition 2. Evaluate PCL If medial femoral contact point exhibits excessive tension and posterior positioning, release anterolateral bundle PCL fibers.
	

[figure not shown]

ORTHOSENSOR® Tel [name] [contact])
Training and Education [contact]

This document contains proprietary and confidential information belonging to OrthoSensor, Inc. Only trained medical personnel should use the OrthoSensor VERASENSE Knee System. OrthoSensor, as the manufacturer of the VERASENSE device, does not practice medicine and does not recommend any particular surgical technique or treatment for use on a specific patient. The surgeon who performs total knee arthroplasty is ultimately responsible for determining and utilizing the appropriate techniques for implanting the prosthesis in each individual patient.

VERASENSE™ ORTHOSENSOR™ SURGICAL TECHNIQUE QUICK REFERENCE

APPROACH TO VALGUS KNEE

▶ TIGHT IN EXTENSION - LATERALLY
	
▶ TIGHT IN FLEXION - LATERALLY
	
▶ TIGHT IN FLEXION AND EXTENSION - LATERALLY
	

SENSOR PRESENTATION:
	
SENSOR PRESENTATION:
	
SENSOR PRESENTATION:
	
SENSOR PRESENTATION:

			

SURGICAL CONSIDERATION:
	
SURGICAL CONSIDERATION:
	
SURGICAL CONSIDERATION:
	
SURGICAL CONSIDERATION:

			

Evaluate Lateral Posterior Capsule & Arcuate
	
Evaluate Popliteus
	
Condition 1. Loads 20-40 lbs.
	
Condition 2. Loads >40 lbs.


Palpate the lateral posterior capsule and/or the arcuate ligament to assess tension; release as necessary.
	
Release tight fibers of the popliteus tendon.
	
Extension Balancing:
 
 - Release posterior lateral corner; recheck loads. - Release posterior lateral capsule and arcuate complex; recheck loads. - Consider releasing tight fibers of IT band, if necessary. 	
If necessary, you may recut tibial plateau to add more valgus.

		
Flexion Balancing:
	

Evaluate IT Band If lateral posterior capsule/arcuate does not fully address tension, consider releasing tight fibers of the IT band.
		
 - If excessive loads are still uncorrected, then popliteus tendon is checked for tension and released. 	

TIGHT EXTENSION GAP
	
ADVERSE FLEXION GAP
		

▶ TIGHT ONLY IN EXTENSION - SYMMETRICALLY
	
▶ TIGHT ONLY IN FLEXION - SYMMETRICALLY
		

SENSOR PRESENTATION:
	
SENSOR PRESENTATION:
	
SENSOR PRESENTATION:
	
SENSOR PRESENTATION:

			

SURGICAL CONSIDERATION:
	
SURGICAL CONSIDERATION:
	
SURGICAL CONSIDERATION:
	
SURGICAL CONSIDERATION:

			

Condition 1. Loads 20-40 lbs. Release posterior capsule.
	
Condition 2. Loads >40 lbs. If necessary, consider recutting distal femur.
	
Loads > 40 lbs. Increase tibial slope.
	
Loads < 10 lbs. Increase thickness of shim.

